6.5.2 Secondary safety variables

6.5.2.1 Endometrial histology (eg, benign endometrium, presence or absence of hyperplasia or malignancy)

For endometrial histology evaluations the following time intervals will be considered:

- Any time point
- Intervals A (according to [Figure 4-1](#))
- Intervals B (according to [Figure 4-1](#))
- Exit examination (according to [Figure 4-1](#))
- Bleeding episode after last TP time windows in subjects with at least 56 days of treatment within the TP (by TP and overall)
 - From start of the subjects' last treatment period until day 55 of the same TP

- From day 56 of the same treatment period until last day of the 1st bleeding episode after TP
- After 1st bleeding episode of the same treatment period, i.e. from 1st day after end of the first bleeding episode to last day of 2nd bleeding episode
- After 2nd bleeding episode of the same treatment period, i.e. from first day after end of 2nd bleeding episode to last day of 3rd bleeding episode
- After 3rd bleeding episode of the same treatment period, i.e. from first day after end of 3rd bleeding episode to last day of 4th bleeding episode

Presentations will be done for

- the safety read (Reader #1 or #5)
- the majority read (Readers #2-4)
- all reads (Readers #1-5)

For the safety read only one result will be available per biopsy (based on either Reader #1 or #5), whereas for the “majority read” and “all reads” more than one reader result needs to be considered.

Analyses will present the number and percentage of either subjects or biopsies. Analyses based on number of subjects will use a worst-case approach within each of the above-mentioned time windows, except “Exit biopsies” where the last available measurement will be used.

Majority read definitions:

Majority read results will only be provided in case biopsy data from Readers #2, #3 and #4 are available.

Majority read will be determined for main results and subcategories (see [Table 6-3](#) [Table 6-3](#)). First, adequacy (for part II and III) or sufficiency (for part IV) of tissue will be investigated. If at least 2 of the 3 readers consider it adequate/sufficient, the majority for the main results will be determined. For the majority main result, the majority of the respective subcategories will be determined. If no majority result is available (3 different results in 3 readers, 2 different results in 2 readers), either “no consensus” or the worst case will be presented. [Table 6-3](#) presents an overview of all biopsy endpoints including the approach which is used in case no majority is available.

For ‘tick all that apply’-subcategories, individual features will be considered the majority in case at least 2 readers have ticked the feature, i.e. for one biopsy more than one subcategory can be the majority.

All read definition:

All read results will be based on all biopsies with results from at least one reader.

A biopsy is considered non-benign in case “Benign endometrium” = “No” or “Endometrial Hyperplasia (2014)” or “Endometrial Hyperplasia (WHO 1994)” or “Malignant Neoplasm” = “Yes”.

Worst case across time interval:

Worst case of biopsies or majority results across time windows is determined for each endpoint in [Table 6-3](#) [Table 6-3](#).

Table 6-3: Overview of biopsy endpoints including majority result handling and worst case

Part		Endpoint	No majority available	Worst case across time intervals for subject based analyses
Main results				
I	Main diagnosis	Adequate endometrial tissue	- (not possible)	“Yes”
II		Benign endometrium Endometrial Hyperplasia (WHO 2014) Malignant Neoplasm	Worst case: List is ordered by severity, from low to high	List is ordered by severity, from low to high
III		Endometrial Polyp	Worst case: yes	“Yes”
IV	PAEC	Tissue sufficient for PAEC read	- (not possible)	“Yes”
		PAEC present	Worst case: yes	“Yes”
Subcategories				
II	Main diagnosis	Benign endometrium (select one) Atrophic Inactive Proliferative Disordered Proliferative Secretory including progestin and OCP effect Menstrual Endometritis Other,specify	“no consensus”	- (will not be presented)
		Endometrial Hyperplasia (WHO 2014) (select one) Hyperplasia without atypia Atypical hyperplasia / Endometrioid Intraepithelial Neoplasia (EIN)	Worst case: Atypical hyperplasia / Endometrioid Intraepithelial Neoplasia (EIN)	Atypical hyperplasia / Endometrioid Intraepithelial Neoplasia (EIN)
III		Endometrial Polyp (select one) Atrophic Functional Hyperplastic	“no consensus”	- (will not be presented)
IV	PAEC	PAEC (tick all that apply) Pre-Decidua Absent Extensive cysts Present Secretory Changes, Extensive Mitoses (required, may be rare) Apoptosis Abnormal Vessels	“no consensus”	- (will not be presented)

PAEC = progesterone receptor modulator-associated endometrial changes; WHO = World Health Organization

6.5.2.2 Endometrial thickness

For endometrial thickness the following time intervals will be considered:

- Intervals A (according to [Figure 4-1](#))
- Intervals C (according to [Figure 4-1](#))
- Exit examination

Number of subjects with ultrasound performed will be presented.

Summary statistics for change from baseline in endometrial thickness will be provided. In addition, the proportion of subjects with endometrial thickness > 18 mm will be investigated. A subgroup analysis by exposure group (treatment duration <=90 days, 91 to 180 days, etc.) will present the proportion of subjects with endometrial thickness > 18 mm and cyst like structure either ovary >= 3cm.

To investigate the correlation of endometrial thickness and biopsy results, the proportion of biopsies with hyperplasia without atypia (WHO 2014), atypical hyperplasia / EIN (WHO 2014), PAEC

present, PAEC not present, Extensive cysts present, and Extensive cysts not present will be presented for endometrial thickness > 18mm in ultrasound and endometrial thickness ≤18 mm in ultrasound.

6.5.2.3 Percentage change from baseline in BMD measured, hip, and femoral neck by DEXA

The percentage change in BMD of hip, and femoral neck will be summarized in the same way as described for the primary safety variable.

6.5.3 Other safety variables

6.5.3.1 Endometrial histology (diagnosis of PAEC, individual features of PAEC)

Diagnosis of PAEC, individual features of PAEC will be analyzed in the same way as Endometrial histology described in section Secondary safety variables (see section 6.5.2.1)

6.5.3.2 Percentage of subjects with BMD decrease >6% and Z-score < -2 measured at the lumbar spine

Frequency table with number and percentage of subjects with BMD decrease >6% and Z-score <-2 measured at the lumbar spine will be displayed by treatment group during treatment period.

6.5.3.3 Change in Z-score over time

The Z-score and the change in Z-score by BMD location will be summarized by treatment group and time intervals using descriptive statistics.

Z-score with frequencies and percentages for the following categories: <-2, ≥-2 - <-1.5, ≥-1.5 - <-1, ≥-1 - ≤0, >0 - ≤1, >1 - ≤1.5, >1.5 - ≤2 and >2 will also be summarized by treatment group.

6.5.3.4 Ovarian cysts

Ovarian cysts will be examined by ultrasound. All scheduled and unscheduled assessments will be considered for the analysis. Three analyses will be performed for ovarian cysts:

- Number of subjects showing cyst like structures with largest diameter > 3 cm in the ovary
- Analysis of ovarian cyst episodes (see below for definition)
- Analysis of AEs associated with ovarian cysts

The analysis of **Number of subjects with ovarian cyst like structures > 3 cm in largest diameter** in ovary will be shown by treatment group and by time intervals A and B (according to [Figure 4-1](#)). One table will be produced for time intervals A and one table for time intervals B.

For each time interval it will be determined whether an individual subject shows cysts like structures with a largest diameter > 3 cm at least once during that time interval.

In addition to the corresponding time intervals, both tables will contain the assessment for 'Exit examination.'

Frequencies for the type of cyst like structures identified will be included in the table. Type of cyst like structures will be shown as recorded in the eCRF: 'Follicle-like structure', 'Corpus luteum cyst', 'Endometrioma' and 'Other'.

The overall assessment for both ovaries will be displayed, and information about ovary laterality will not be included in the table.

If cyst like structures > 3 cm are visualized in the ovaries, unscheduled ultrasound examinations should be performed at least every 4 weeks to document the regression or outcome. An **ovarian cyst episode** is defined as the time period from occurrence of a cyst like structure > 3 cm until its resolution. Ovarian cyst episodes will only take account of the occurrence of follicle-like structures and corpus luteum cysts. Two different definitions of “resolution” are used in the analysis:

- the subject does not show in the same ovary (left or right) a cyst like structure of the same type
- the subject does not show in the same ovary (left or right) a cyst like structure of the same type with diameter ≤ 3 cm.

For both definitions, the date of the first observation of the cyst like structure is the **start of the episode**. The date when the cyst like structure appears for the first time as resolved (absence of cyst like structure or cyst like structure with diameter ≤ 3 cm) is considered the **end of the episode**. The length of time between start and end of the episode is the **duration of the episode**.

If the cyst resolution does not occur, then the length of time between the start of the episode and the last observation will be considered the cyst episode duration.

If only the start of the episode is recorded but no follow-up has been performed, then the duration of the episode is unknown.

The analysis will include cysts episodes occurring in both ovaries with no distinction of ovary laterality (left or right). Although the information of ovary laterality will not be displayed in the table, it will be critical to monitor the progression of individual cyst like structures.

The time intervals A and B (according to [Figure 4-1](#)) will be considered, therefore two sets of tables will be produced. Ovarian cyst episodes will be assigned to the time interval when the start of the episode occurs.

Two analyses will be produced for ovarian cyst episodes:

- Number of subjects with at least one ovarian cyst episode by time intervals.
- Number of ovarian cyst episodes by time intervals including: i) summary statistics of ovarian cyst episode duration, ii) by categorization of the duration by 4-week intervals, and iii) summary statistics of largest diameter of the cyst like structure per episode and per time interval.

Two tables will be produced for these two analyses, one for each definition of cyst episode resolution.

The analysis of **adverse events related to ovarian cysts** by time intervals will include AEs identified by the Bayer MedDRA query (BMQ) for ‘Benign ovarian cyst and associated complications’ [V21],], which include the preferred terms (PTs): Haemorrhagic ovarian cyst, Ovarian cyst, Ovarian cyst ruptured and Ovarian cyst torsion.

The table will show number of subjects with AEs, non-serious AE and SAEs. For each one of these AE categories the table will include severity, whether the AE led to drug withdrawal and AE duration. In addition, SAEs will include the reason for being classified as serious as recorded in the eCRF.

The analysis will be shown by treatment group and will be done for pre-treatment AEs, TEAEs and post-treatment AE. AEs will be assigned to the time interval when the AE starts. AEs with onset during a treatment period or up to 8 days after last drug intake in any treatment period will be considered 'on-treatment'. AEs with onset after date of last study drug intake in any treatment period + 8 days and before the start of the next treatment period will be considered 'off-treatment'. The summary table for TEAEs will be presented by overall AEs, on-treatment AEs and off-treatment AEs.

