6.2.3.2 Time to event related variables

- Time to onset of amenorrhea for each treatment period
- Time to onset of controlled bleeding for each treatment period
- Time to start of bleeding after last study drug intake (assessed by the UF-DBD).

Time to event related variables and censoring rules are defined in [Section 4.5](#).

Time to onset variables will be analyzed using the Kaplan-Meier estimates (including number of events, number of censored, 25th, median, and 75th percentiles). This analysis will be performed using the calendar time (days) as unit. Kaplan-Meier plots will also be presented. The analysis will be done by treatment group and TP (time intervals B according to [Figure 2](#), excluding screening and FUP). For treatment group A2, TP per 168-day defined in the protocol will be used and shown separately.

Time to start of bleeding after last study drug intake for treatment group B will not be analyzed.

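### Unresolved ovarian cyst episodes are pooled with resolved ones at their last scan and not counted, so the duration summary is biased downward relative to full follow-up

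*SAP*

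**What the plan says.** SAP section 6.5.3.4 states that an ovarian cyst episode "is defined as the time period from occurrence of a cyst like structure > 3 cm until its resolution". The episode ends on the date of the first examination showing resolution, under either of two definitions of resolution. While a cyst above 3 cm is present, "unscheduled ultrasound examinations should be performed at least every 4 weeks to document the regression or outcome".

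Two rules cover episodes without an observed end:

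- Followed but not resolved: "the length of time between the start of the episode and the last observation will be considered the cyst episode duration".
- No scan after the first: "If only the start of the episode is recorded but no follow-up has been performed, then the duration of the episode is unknown".

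The episode table, produced once per resolution definition, then gives "i) summary statistics of ovarian cyst episode duration, ii) by categorization of the duration by 4-week intervals". The section provides no censoring, no count of unresolved episodes and no separate display of them.

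Elsewhere the SAP does censor. Section 6.2.3.2 says "Time to onset variables will be analyzed using the Kaplan-Meier estimates (including number of events, number of censored, 25th, median, and 75th percentiles"), with censoring rules in section 4.5. Section 6.5.3.10 censors subjects who do not reach ALT above three times the upper limit of normal.

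**The concern.** For a cyst still present at the last scan, the time to that scan is a lower bound on the duration. The SAP enters it as a completed duration. A cyst present at a last scan in week 4 and a cyst found to be gone in week 4 give the same value and fall in the same 4-week category. The table offers no way to tell them apart or to see how many there are.

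What is at stake is the description of how long cysts persist, which is the purpose of the repeat scans. Persistent cysts are the ones most likely to be unresolved at the last observation, so the upper end of the distribution is the part most distorted.

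**Working it through.** The SAP gives no expected duration, unresolved share or length of cyst follow-up, so there is no figure of its own to reproduce. What follows is illustration under stated assumptions.

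**Direction.** For a given episode let T be the duration that would be recorded if scanning continued until resolution, and C the time of the last scan. The SAP records min(T, C), which never exceeds T. Replacing T by min(T, C) across the same episodes can therefore only lower, or leave unchanged, the mean, each quantile and the share above any cut-off.

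**Size with a fixed follow-up.** Assumptions: T exponential with mean m weeks, every episode followed for F weeks, times known exactly. The values F = 12 and F = 24 are borrowed from the post-treatment follow-up planned in section 3 for Subgroups 2 and 1. They are not limits that the SAP sets on following a cyst.

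- Censored share = exp(−F/m)
- Mean under the SAP rule = m × (1 − exp(−F/m))

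| True mean m | F | Censored share | Mean under SAP rule |
|---|---|---|---|
| 8 | 12 | exp(−1.5) = 22% | 8 × 0.777 = 6.2 |
| 8 | 24 | exp(−3) = 5% | 8 × 0.950 = 7.6 |
| 12 | 12 | exp(−1) = 37% | 12 × 0.632 = 7.6 |
| 12 | 24 | exp(−2) = 14% | 12 × 0.865 = 10.4 |

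Under these assumptions the mean is low by exactly the censored share.

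**Size with variable follow-up.** A simulation of 40,000 episodes per setting took m = 8 weeks and independent exponential censoring. At 10 / 20 / 30 / 50% unresolved, the SAP-rule mean was 7.3 / 6.4 / 5.6 / 4.0 weeks and the SAP-rule median 5.0 / 4.4 / 3.9 / 2.8 weeks. The Kaplan-Meier median stayed at 5.5 to 5.6 weeks, against a true median of about 5.5.

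**Effect of 4-weekly scans.** Suppose resolution is dated at the next 4-weekly scan.

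- With full follow-up and m = 8, the mean recorded duration is 4 / (1 − exp(−4/8)) = 4 / 0.393 = 10.2 weeks. This already exceeds the true 8 because of the wait for the next scan.
- In the simulation, the SAP rule gave 9.5 / 8.6 / 7.8 / 6.3 weeks when 8 / 15 / 23 / 38% of followed episodes were unresolved.
- The share recorded as longer than 8 weeks fell from 37% to 33 / 29 / 24 / 13%.

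Against the proper comparator of about 10.2 weeks, every SAP-rule mean is low. Against the true 8 weeks, some lie above and some below.

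**The case against.** Several points on the other side have weight.

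- **Durations shorter than the truth.** A reader might infer that the reported durations understate how long cysts really last. The SAP does not support that. Dating resolution at the next scan lengthens resolved episodes by up to one scan interval, while dating the start at first observation shortens them. In the simulation with 15% unresolved, the SAP-rule mean was 8.6 weeks against a true 8.0. The downward bias is established only relative to full follow-up on the same scan schedule.
- **A biased group comparison.** A reader might also infer this from section 3: under Amendment 9 vilaprisan courses were cut short while group B could continue. But repeat scans are tied to the presence of a cyst, not to treatment, and Amendment 10 asks treated subjects, including those who had completed or discontinued, to return for safety evaluation. No cyst follow-up by group is given, so a differential bias is possible but not shown.
- **The no-follow-up rule.** Treating such an episode so that "then the duration of the episode is unknown" is not a defect. Nothing is imputed, and a Kaplan-Meier analysis would gain nothing from it.
- **Persistence is partly shown elsewhere.** The occurrence tables include the exit examination, so subjects still showing a cyst above 3 cm at the end are counted. That count is not linked to episodes, so it does not repair the duration table.
- **Limited weight.** This is a descriptive variable with no test or decision rule attached.

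These points limit the direction, size and reach of the concern. None of them makes a lower bound a completed duration.

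**Conclusion.** The point stands in a bounded form. Section 6.5.3.4 pools right-censored times with complete durations and does not count the unresolved episodes. The duration summaries, and the share in long categories, are therefore biased downward relative to full follow-up on the same scan schedule.

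The size cannot be computed from the SAP. Under exponential durations the shortfall in the mean equals the unresolved share: 5% to 37% across the fixed follow-up cases above, and up to 50% if half the episodes are unresolved. These figures rest on the assumed distribution, on censoring independent of duration and on assumed lengths of follow-up.

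The table is worth correcting because the SAP already applies the right method to comparable data. The primary BMD analysis is not touched.

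**What to change.** In section 6.5.3.4:

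1. Treat an unresolved episode as censored at its last ultrasound.
2. By treatment group and for each resolution definition, report the number of episodes resolved and unresolved, and Kaplan-Meier quartiles of time to the first scan showing resolution.
3. Restrict the simple duration statistics and 4-week categories to resolved episodes, or show unresolved ones in separate rows.
4. Keep episodes with no follow-up scan as unknown, and report how many there are.
5. State in a footnote that resolution is dated at scans and that a subject may contribute several episodes. If confidence intervals are given, use a variance clustered by subject.

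No new data are needed: the start date, the last observation date and the resolution status are already required by the current rules. The cost is a few lines of SAP text and a somewhat longer table. If only a minimal change is possible, counting unresolved episodes and summarising them separately removes the main ambiguity.

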6.5.3.5 AEs

All AEs will be coded by MedDRA terms (current version at time point of analysis) and classified into pre-treatment AEs, treatment-emergent (TEAE) and post-treatment AEs.

All AEs will be flagged as treatment-emergent adverse event (TEAE) except all AEs where there is clear evidence that the event starts before date of first study drug exposure (pre-treatment AEs) or after the date of last study drug exposure + 60 days (post-treatment AE). For Treatment group B, the reference start/end dates (as defined in section 4.5 Data Rules) will be used for this derivation, rather than date of first study drug exposure/ date of last study drug exposure. AEs with clear evidence of start before the date of first study drug exposure are flagged as pre-treatment AE unless the AE worsens at or after the date of first study drug exposure and before or at the date of last study drug exposure + 60 days. AEs starting before but worsening at or after the date of first study drug exposure and before or at the date of last study drug exposure + 60 days will be considered as two events, a pre-treatment AE and a TEAE. The pre-treatment AE will stop at the time of worsening and the new TEAE will start at the time of worsening. Same applies in case an AE starts at or after the date of first study drug administration, but before the date of last study drug administration + 60 days and worsens afterwards then e.g. leading to a TEAE and a post-treatment AE.

Reasons for worsening of an AE are listed below.

- AE intensity/grade is worsened (e.g.: moderate to severe)
- AE changed to a serious event
- AE ends with death
- AE is drug-related

TEAEs will further be categorized into on-treatment and off-treatment events.

All TEAEs should be flagged as on-treatment events except all TEAEs where there is clear evidence that the event starts outside all on-treatment phases. Each on-treatment phase starts with the date of first study drug exposure and ends with the date of last study drug exposure during a treatment period plus 8 days. For subjects in the VPR-6/2 treatment group, TEAEs with an onset within 8 days after end of TP1 (or TP3 or any TP with an odd number), but after start of TP2 (TP4 or after any TP with even number) will be reported as on-treatment for TP2 (TP4 and so on).

TEAEs with clear evidence of start outside all on-treatment phases will be flagged as off-treatment events unless the TEAE worsens during an on-treatment phase. TEAEs starting during off/on-treatment phase, but worsening during an on/off-treatment phase will be considered as two events, an off/on-treatment TEAE and an on/off-treatment TEAE. The off/on-treatment TEAE will stop at the time of worsening and the on/off-treatment TEAE will start at the time of worsening.

Imputation

Missing “Causality to Protocol Procedure” will be imputed with “yes” in case “Causality to study drug” is “no”, and with “no” in case “Causality to study drug” is “yes”.

Presentation

The tabulation will follow in principle the Bayer Global Standard Tables catalogue (currently V 4.0 default), with the necessary modifications like for on- and off-treatment TEAEs.

Adverse events of special interest (AESIs) will be identified in two different ways

- 1) The investigators will assess all AEs to determine if they are AEs of special interest (AESIs) and document this in the eCRF. The following AEs are included:
 - a. HMB
 - b. Liver disorders
 - c. Endometrial disorders
 - d. Skin disorders
 - e. Adrenal disorders
 - f. Relevant loss of BMD during treatment
- 2) Adverse events will be categorized into AE groupings of special interest based on MedDRA groupings as defined within expert statement for compound vilaprisan (Selection of coding conditions applicable for AESIs as defined in the study protocols of vilaprisan phase II/III studies). List of AESIs in current expert statement based on MedDRA Version 22.1 is provided in Appendix 3.

AESIs based on investigator assessment and AESIs based on MedDRA groupings will be presented separately. They will be presented by AESI group (if available), MedDRA primary SOC and PT and study drug. Summary tables for AESIs by maximum intensity and by worst outcome will be produced. Furthermore, listings will be provided.

